2.1.3 Selected Other Secondary Objectives

1. To estimate the average duration of remission among participants.
2. To estimate the average time to first response among participants.
3. To estimate the average duration of response among participants.
4. To estimate the proportion of participants who maintain a state of remission from week 16 through week 52.

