2.2.1 Primary Endpoint/Variable: Remission

In general use of rescue medication is considered as treatment failure (not achieving remission or response) if there are any new use of rescue medication to treat CD or increased rescue medication dose from baseline prior to any remission or response assessment. Please refer to section 6.1.6 for more details.

The primary variable is the proportion of subjects who experienced remission at Week 16 after the initiation of open-label phase, where remission is defined as a subject having a Crohn's Disease Activity Index (CDAI) score of <150 . Subjects who have a Week 16 CDAI measurement ≥ 150 or who do not have a CDAI measurement at Week 16 will be classified as not having achieved remission at that time point. Initiation of open-label phase is the first dosing time of open-label phase and from here and after it would be reference as initiation.

The CDAI is used to assess the activity of CD; higher scores indicate more active disease.

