2.2.3 Selected Other Secondary Endpoints/Variables

- Time to remission – Number of weeks after initiation that a subject first records a state of remission (CDAI score < 150). It will be calculated as the date on which remission is first observed minus the date of the first dosing date plus 1 day, divided by 7. For subjects still on study and not achieved remission at the time of assessment, time to remission will be censored at the date of the last assessment of CDAI score.
- Duration of remission – The number of weeks the subject is in remission (CDAI score < 150). It will be calculated as the first date following remission at which CDAI is ≥ 150 minus the date of remission, plus 1 day, divided by 7. Those subjects who experienced remission and continue to be in remission at the time of their last CDAI assessment will be censored at the date of their last CDAI assessment. Duration of remission will be calculated only for patients achieving remission.
- Time to response – Number of weeks after initiation that a subject first achieves a state of response (a reduction from baseline of ≥ 100 in CDAI score). It will be calculated as the date on which response is first observed minus the date of the first dose, plus 1 day, divided by 7. For those subjects who have not experienced response, time to response will be censored at the date of the last assessment of CDAI score.
- Duration of response – Time in weeks that a subject is in a state of response (a reduction from baseline of ≥ 100 in CDAI score). It will be calculated as the first date following response at which the reduction from baseline in CDAI is < 100 minus the date of response, plus 1 day, divided by 7. Those subjects who experienced response and continue to be in response at the time of their last CDAI assessment will be censored at the date of their last CDAI assessment. Duration of response will be calculated only for patients achieved response.
- Proportion of subjects experienced maintenance of remission (CDAI score < 150) from week 16 through week 52. Subjects experiencing a CDAI score ≥ 150 at any visit time point assessment between week 16 and week 52 or have no CDAI measurement week 16 or week 52 will be considered as having not achieved maintenance of remission.

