6.1.3 Missing Data and Handling of Dropouts

All available outcome and safety data will be included in data listings and tabulations.

CDAI Missing Data:

The computation of CDAI requires 7 days of consecutive diary daily data. For subjects with CDAI diary data reported that is less than 7 days of data, the reported data will be standardized to 7 days by dividing the sum of CDAI score over the number of days of data by total number of days of reported data multiplied by 7. If less than 4 days of diary data is available, the subject will be categorized as a non-responder and the CDAI score will be considered missing. As specified in section 2.2, subjects with missing assessment will be assumed to not be in a state of remission/success for each scheduled visit (week 16, 26, or 52).

Handling of missing date information for AEs:

The term *missing date* refers to a completely missing date or to partial date where month or/and day or/and year is/are missing, e.g. missing month/day/year. Missing start and end dates will be imputed conservatively, i.e. missing values will be imputed in such a way that the duration of the AE is considered with the longest possible duration. The missing start date and end date of AE will be imputed for the purpose of defining treatment emergent adverse events (TEAE) and for assigning events to treatment periods using the following definitions:

(i) Adverse Event Start Date:

Event Missing Day: If Adverse event day is missing but month and year present, then impute the 1st of the month unless month and year are the same as first dose of study drug then impute day first day of dose.

Event Missing day and month – If adverse event day and month both are missing but year is present then impute 1st January unless year is the same as first dose date then impute day and month first dose day and month.

Completely missing – impute first dose date unless the end date suggests it could have started prior to this in which case impute the 1st January of the same year as the end date.

(ii) Adverse Event End Date:

Missing day – If AE day is missing but month and year is present then impute the last day of the month.

Missing day and month – If AE has missing day and month but year is present then impute 31st December.

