6.1.6 Rescue Medications Use

Subjects rescued with the following treatments or whose baseline doses/regimens are increased to treat new or unresolved CD symptoms may remain on the study drug at the discretion of the investigator and continue to be assessed at all scheduled study visits:

- Oral or rectal 5-ASA compounds
- Azathioprine or 6-mercaptopurine (6-MP) or methotrexate
- Total parenteral nutrition as treatment of CD
- Systemic or rectal corticosteroid therapy
- Anti-TNF or other biologic agent

In analyses of remission or response, subjects who initiate new treatment or increase concomitant medication to treat CD symptoms will be considered as treatment failures.

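### Duration of remission and of response is censored at the last qualifying CDAI whatever the reason for leaving, so it may be overstated if some subjects withdraw for worsening Crohn's disease without a failing CDAI

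*SAP*

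**What the plan says.** Average duration of remission and of response are named objectives in SAP 2.1.3 ("To estimate the average duration of remission among participants", with a parallel item for response). SAP 2.2.3 measures a remission up to the "first date following remission at which CDAI is ≥ 150 minus the date of remission"; no other event ends it. Remitters who "continue to be in remission at the time of their last CDAI assessment will be censored at the date of their last CDAI assessment". For response, those who "continue to be in response at the time of their last CDAI assessment will be censored" in the same way. Neither definition refers to the reason for leaving, or to rescue medication.

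Three other rules treat comparable subjects as failures:
- Maintenance of remission, in the same section: subjects who "have no CDAI measurement week 16 or week 52 will be considered as having not achieved maintenance of remission".
- SAP 6.1.3: "subjects with missing assessment will be assumed to not be in a state of remission/success for each scheduled visit", with weeks 16, 26 and 52 listed.
- SAP 6.1.6: in remission or response analyses, "subjects who initiate new treatment or increase concomitant medication to treat CD symptoms will be considered as treatment failures". SAP 2.2.1 applies this to new use, or an "increased rescue medication dose from baseline prior to any remission or response assessment".

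SAP 6.3.3.1 analyses the durations by Kaplan-Meier, by parent-study treatment, anti-TNF use and overall, with a log-rank comparison of the parent-study groups. The schedule in SAP 4.1.1 marks CDAI at screening and at weeks 8, 16, 26, 39, 52 and 56, and has no early-termination column. SAP 6.2.1 summarises reasons for withdrawal. The only sensitivity analysis described (6.3.1) concerns week 16 remission.

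**The concern.** Kaplan-Meier assumes that a censored subject has the same later risk of relapse as those still followed. A subject who leaves because the disease has flared does not. The relapse has happened, or is happening, but no CDAI of 150 or more exists to record it.

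On-treatment CDAI visits are 8, 10, 13 and 13 weeks apart, so there is room to relapse and leave between two scores. Suppose a subject first remits at week 16, flares, and leaves at week 22 with no further CDAI. Duration is censored at the week 16 date. The same subject fails maintenance and counts as not in remission at weeks 26 and 52. The report would then show, side by side, a duration curve and a maintenance proportion that treat this subject in opposite ways. Any error in the curve makes remission look longer.

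**Working it through.** **1. The plan's own figure.** SAP 6.1.7 gives a maximum Clopper-Pearson width of 0.203 for 100 subjects. For 50/100 the limits are 0.3983 and 0.6017, a width of 0.2034, so the figure reproduces. It concerns proportions. The documents give no design figure for durations or withdrawal, so the rates below are assumptions.

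**2. One subject.** Duration = (end date - start date + 1 day)/7. If the first remission CDAI is also the last, this is (0 + 1)/7 = 0.14 weeks, censored. If remission began at week 8 and the last CDAI was at week 16, it is (56 + 1)/7 = 8.14 weeks, censored.

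**3. Twenty week 16 remitters (invented).** Four relapse at week 26, four withdraw for worsening after a week 26 CDAI below 150, three relapse at week 39, and nine complete week 52 in remission.
- SAP rule: (1 - 4/20) x (1 - 3/12) = 0.80 x 0.75 = 0.60; median not reached.
- Withdrawals as events at the next visit: (1 - 4/20) x (1 - 7/16) = 0.80 x 0.5625 = 0.45; median 23.1 weeks. Dating them between the two visits gives 0.80 x (1 - 4/16) x (1 - 3/12) = 0.45 as well.
- Maintenance: 9/20 = 0.45.

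**4. A grid of rates.** The cohort is week 16 remitters with CDAI at weeks 26, 39 and 52. In each interval a fraction r has an observed relapse, a fraction w withdraws without a CDAI, and a share s of those withdrawals is for worsening. At 36 weeks:
- SAP rule: S = [1 - r/(1 - w)]^3
- Worsening withdrawals as events: S = [1 - (r + sw)/(1 - (1 - s)w)]^3
- Maintenance: (1 - r - w)^3

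| r, w, s | SAP rule | As events | Gap | Maintenance |
|---|---|---|---|---|
| 0.20, 0.05, 0.25 (smallest gap) | 0.492 | 0.473 | 0.019 | 0.422 |
| 0.15, 0.10, 0.50 (middle) | 0.579 | 0.492 | 0.087 | 0.422 |
| 0.10, 0.15, 1.00 (largest gap) | 0.687 | 0.422 | 0.265 | 0.422 |

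Middle case: 1 - 0.15/0.90 = 0.8333, cubed 0.579; 1 - 0.20/0.95 = 0.7895, cubed 0.492. Over r = 0.10-0.20, w = 0.05-0.15 and s = 0.25-1 (27 combinations) the SAP rule is higher every time, by 0.02 to 0.27. Setting s = 0 makes the two formulas identical, so there is no bias if no withdrawal is for worsening.

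**5. Simulation on the trial's visit schedule.** Assumed: 40 remitters, first remission at weeks 8/16/26/39 in 40/35/15/10%, relapse hazard 0.015 or 0.025 per week, and a share q of relapsers leaving mid-interval with no CDAI. Share still in remission at 24 weeks, SAP rule v withdrawal counted as the end:

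| q | Hazard 0.015 | Gap/SE | Hazard 0.025 | Gap/SE |
|---|---|---|---|---|
| 10% | 77% v 75% | 0.30 | 64% v 62% | 0.34 |
| 25% | 79% v 74% | 0.81 | 68% v 61% | 0.92 |
| 50% | 85% v 74% | 1.96 | 76% v 60% | 2.10 |

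A repeat run agreed to within about a point, with gaps of about 2-3 points at q = 10% and 5-7 at q = 25%. With 20 remitters the gaps are unchanged and the standard error grows by the square root of 2. The lower ratios become 0.30/1.414 = 0.21 at q = 10% and 0.81/1.414 = 0.57 at q = 25%.

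**The case against.** The strongest objection is that nothing shows the bias will occur. The documents give no withdrawal rate, and if withdrawals are unrelated to disease course, censoring is harmless. This stands: the overstatement is conditional.

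A failing CDAI may also be obtained at exit. The protocol reviewed is a synopsis, and the SAP abbreviation list includes early termination. A CDAI of 150 or more at such a visit would already end the remission under 2.2.3. This stands too, although the schedule shows no such visit. The diary is tied to the 7 days before a planned visit, and 6.1.3 treats fewer than four diary days as a missing CDAI, so an unplanned exit may not give a usable score.

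Rescued subjects may stay on study drug and be assessed (6.1.6), which argues against large values of q. But 6.1.6 gives no event date for the durations and does not reach a subject who leaves with no later CDAI. It also leaves unclear how a rescued subject whose CDAI stays below 150 enters the duration analysis.

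A reader might infer that the SAP contradicts itself. The documents do not support that. Maintenance is a proportion of all ITT subjects; duration is a time-to-event summary among remitters. Imputing failure for one and censoring for the other is a possible choice, and response has no maintenance endpoint to compare.

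Finally, these are lower-order, mainly descriptive endpoints. The protocol's statistical section foresaw Kaplan-Meier curves for measures no more than 4 weeks apart, so durations from visits 8-13 weeks apart are coarse under any censoring rule. That limits the priority of the point but does not remove the directional error.

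**Conclusion.** The concern holds as a conditional one. The 2.2.3 rule biases both durations upward whenever some subjects leave for worsening Crohn's disease with no failing CDAI at exit, and no planned analysis would show it. On the assumptions in step 5, the 24-week gap is about 2-3 points (0.2-0.4 SE) at q = 10% and about 5-7 points (0.6-0.9 SE) at q = 25%, for 20 to 40 remitters. It reaches about 2 SE with 40 remitters only if half of all relapsers leave unmeasured, and nothing in the documents supports so high a share.

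The stronger statement, that the durations are overstated, is not supported: it needs a withdrawal pattern and an absence of exit CDAI that the documents do not establish. For remission, the rule also sits oddly beside the maintenance and missing-visit rules. The primary and key secondary endpoints are not affected. This is an inexpensive improvement worth making, not a flaw that undermines the trial.

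**What to change.** In SAP 2.2.3, for both durations, define the end of remission or response as the earliest of:
- (a) a CDAI that no longer meets the definition, including any CDAI taken at early termination, which is used first;
- (b) withdrawal with a recorded reason of lack of efficacy or worsening Crohn's disease;
- (c) new or increased Crohn's medication already classed as treatment failure in 6.1.6.

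Prespecify one event date for (b) and (c), for example the date of withdrawal or of the medication change. Completers and all other withdrawals stay censored at the last CDAI. Report the current all-censored version as a sensitivity analysis, and state in 6.1.3 and 6.1.6 how those rules apply to the durations.

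The cost is a few sentences and some programming. Withdrawal reasons are already summarised under 6.2.1, but the SAP lists no categories there, so the qualifying ones should be fixed before database lock. Downsides: the result relies on the recorded reason in an open-label study; events under (b) and (c) are dated more finely than relapses found at visits; and durations will be somewhat shorter. Subjects who withdraw for unrelated reasons will still fail maintenance while being censored for duration, so the two endpoints will not match exactly.

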6.3.3 Selected Other Secondary Endpoints/Variables

6.3.3.1 Time to Event Endpoints/Variables Analysis

The Time to event endpoints that will be analyzed includes:

- Time to remission
- Duration of remission
- Time to response
- Duration of response

Kaplan Meier survival curves and parameters showing time-to-first observed response outcome will be summarized by parent study treatment, by anti-TNF use and overall. Summary statistics that will be presented will include minimum, maximum, the 25th and 75th percentiles, 95%

confidence intervals on the median (using the method of Brookmeyer and Crowley), and proportion of the events and censored data. Parent study treatment comparison will be performed using log-rank test.

Kaplan-Meier plots with descriptive summary statistics will be presented.

6.3.3.2 Remission from Week 16 through week 52

Number and proportion of subjects experiencing maintenance of remission (CDAI score < 150) from week 16 through week 52 and the number and proportion of subjects experiencing remission at week 16 and week 52 will be provided within each parent study treatment group and overall, as well as subgroup by anti-TNF agent use. 95% exact Clopper-Pearson confidence interval (CI) for the proportion will also be presented. Parent study treatment comparison will be performed using Fisher's exact test.

In addition, similar summaries will be provided for remission at week 52 overall and for subjects who achieved remission at week 16

Proportion of subjects who achieved the following response will be provided overall and by parent study treatment:

Remission at week 16 plus 50% reduction in CRP or calprotectin from baseline

Remission at week 52 plus 50% reduction in CRP or calprotectin from baseline

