Table 14.2.3.2	Remission at Week 16 and Week 52: Intent-to-Treat Population
Table 14.2.3.3.1	Remission at Week 52: Intent-to-Treat Population
Figure 14.2.3.3.1	Forest Plots of Week 52:Remission Odds Ratio of Parent Study Treatment RHB-104 vs Place by Selected Baseline Biomarker Categories: Intent-to-Treat Population
Table 14.2.3.3.2	Remission at Week 52 for Subjects with Baseline SES-CD ≥ 6 or Calprotectin(mcg/g) ≥ 250 or CRP (mg/dL) ≥ 2.87 Intent-to-Treat Population
Table 14.2.3.3.3	Remission at Week 52 and at least 50% Reduction in CRP or Calprotectin from Baseline: Intent-to-Treat Population: Intent-to-Treat Population
Table 14.2.3.3.4	Remission at Week 52 and at least 50% Reduction in CRP or Calprotectin from Baseline for Subjects with Baseline SES-CD ≥ 6 or Calprotectin(mcg/g) ≥ 250 or CRP(mg/dL) ≥ 2.87 : Intent-to-Treat Population
Table 14.2.3.3.5	Remission at Week 52 by Baseline MAP Buffy Coat Culture Status: Intent-to-Treat Population
Table 14.2.3.3.6	Remission at Week 52 by Week 52 MAP Buffy Coat Culture Status: Intent-to-Treat Population
Table 14.2.4.1	Time to Remission: Intent-to-Treat Population
Table 14.2.4.2	Duration of Remission: Intent-to-Treat Population
Table 14.2.4.3	Time to Response: Intent-to-Treat Population
Table 14.2.4.4	Duration of Response: Intent-to-Treat Population
Figure 14.2.4.1	Time to Remission Kaplan Meier Survival Curve: Intent-to-Treat Population
Figure 14.2.4.2	Duration of Remission Kaplan Meier Survival Curve: Intent-to-Treat Population
Figure 14.2.4.3	Time to Response Kaplan Meier Survival Curve: Intent-to-Treat Population
Figure 14.2.4.4	Duration of Response Kaplan Meier Survival Curve: Intent-to-Treat Population
Selected Other Secondary Outcome Endpoints	
Map PCR Blood Assay and MAP Blood Culture	
Table 14.2.5.1	Summary of MAP Buffy Coat Culture by Visit: Intent-to-Treat Population
Table 14.2.5.2	Shift in MAP Buffy Coat Culture from Baseline to Weeks 16, 26 and 52
Endoscopic Assessments	
Table 14.2.6.1	Baseline and Change from Baseline to Weeks 16 and 52 in SES-CD Total Scores: Intent-to-Treat Population
Table 14.2.6.2	Endoscopic Response: 25% reduction in SES-CD Total Score from baseline to

	weeks 16 and 52: Intent-to-Treat Population
Table 14.2.6.3	Endoscopic Response: 50% reduction in SES-CD Total Score from baseline to weeks 16 and 52: Intent-to-Treat Population
Quality of Life Assessment	

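### Duration of remission and of response is calculated only in subjects who reached the state, then log-rank tested between parent groups under an Intent-to-Treat title, while the objectives ask for the average among participants

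*SAP*

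**What the plan says.** The objectives in SAP 2.1.3, which match the protocol's Objectives, include "To estimate the average duration of remission among participants" (objective 1) and "To estimate the average duration of response among participants" (objective 3).

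SAP 2.2.3 measures each duration from first entry into the state to first loss of it, censored at the last CDAI assessment. It restricts the set twice: "Duration of remission will be calculated only for patients achieving remission" and "Duration of response will be calculated only for patients achieved response".

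SAP 6.3.3.1 lists both durations beside time to remission and time to response. It plans Kaplan-Meier summaries by parent treatment, by anti-TNF use and overall, and then adds, with no exception for the durations: "Parent study treatment comparison will be performed using log-rank test". The statistics it names are the extremes, the quartiles, a confidence interval on the median, and the proportions of events and censored data. It names no mean.

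SAP 6.3 bases the outcome analyses on all ITT subjects, and section 5 defines ITT as everyone enrolled who signed consent. The tables in 8.1 are titled "Duration of Remission: Intent-to-Treat Population" and "Duration of Response: Intent-to-Treat Population"; Figures 14.2.4.2 and 14.2.4.4 carry the same population label.

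The protocol's Statistical Considerations say that no formal between-group comparison will be made, because this study involves no randomization. SAP 6.5, which lists changes from the protocol's methods, does not mention the added test.

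**The concern.** The objective, the definition and the population label do not describe the same quantity. An average among participants, read literally, includes those who spent no time in remission. The definition leaves them out, while the table title says that everyone is in.

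The description of remitters does little harm by itself. The test is the larger problem. A log-rank comparison of durations in remitters has as its null an equal hazard of losing remission, given that remission occurred. The subjects compared are selected by an outcome seen after entry, and the selection can differ between the parent groups. If one group gains extra, shorter remissions, those subjects pull its duration curve down, whereas they would not have entered the comparison had they never remitted. A reader of an ITT-titled table with a p-value could then conclude that the group with more total time in remission did worse.

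**Working it through.** **Plan's own figures.** The SAP gives none for the duration endpoints. Its only precision figure (6.1.7) is a maximum exact 95% interval width of 0.203 for 100 subjects at 50%. It reproduces: the limits are 0.3983 and 0.6017, width 0.2034. It has no bearing on duration.

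**Inputs.** From the documents: 100 subjects planned (SAP 6.1.7) and CDAI at weeks 8, 16, 26, 39, 52 and 56 (SAP 4.1.1). Assumed, because the documents do not state them: 50 per parent group, all remission and relapse rates, and a two-sided 5% level. The extra day in the SAP's duration formula is ignored.

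**Identity.** Mean weeks per participant = (proportion who remit) × (mean weeks among remitters). The remitter-only analysis carries information on the second factor only.

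**Hand example.**
- Group A: 30 of 50 remit at week 16; 15 stay in remission to week 52 (36 weeks, censored) and 15 lose it at week 26 (10 weeks).
- Group B: 12 of 50 remit at week 16; 10 last 36 weeks (censored) and 2 last 10 weeks.
- Per participant: A = (15×36 + 15×10)/50 = 690/50 = 13.8 weeks; B = (10×36 + 2×10)/50 = 380/50 = 7.6 weeks.
- Among remitters: A = 690/30 = 23.0 weeks; B = 380/12 = 31.7 weeks.
- Log-rank among remitters, with one event time at 10 weeks, 42 at risk and 17 losses: observed in A 15; expected 17×30/42 = 12.14; variance 17×(30/42)×(12/42)×(25/41) = 2.115; z = 2.86/1.454 = 1.96, p = 0.049, in favour of B.

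The ordering reverses: A has almost twice B's time in remission per participant and loses the test.

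**Simulation, reversal case.** 50 per group; CDAI at weeks 8, 16, 26, 39 and 52; remission first seen at week 8, 16 or 26 with probability 50%, 35% and 15%; exponential durations; no dropout. Both groups have 20% durable remitters (mean 60 weeks); one group has a further 20% brief remitters (mean 6 weeks).
- Mean among remitters: about 21.8 weeks against 31.0.
- Mean per participant: 0.40×21.8 = 8.7 weeks against 0.20×31.0 = 6.2.
- The remitter-only log-rank rejects in about 36% of trials (35% to 36% over separate runs of 2,000 to 4,000), almost always against the group with more time in remission.

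**Simulation, rate difference only.** 40% against 20% remit, with the same durations (mean 30 weeks). Per participant: 0.40×25.8 = 10.3 weeks against 0.20×25.8 = 5.2. The remitter-only log-rank rejects in about 5% to 6% of trials, which is its nominal level.

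**Range.** Remission starts at week 16 and CDAI is read at weeks 26, 39, 52 and 56. Group B has 20% to 30% remitters relapsing at 0.01 per week. Group A has the same plus 10 to 30 points more, relapsing at 0.03 to 0.12 per week. A has 1.4 to 8.3 more mean weeks per participant in every setting, yet the log-rank significantly favours B in 7% to 63% of trials and favours A in under 1%.

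**Calibration.** With identical groups the log-rank rejects in about 5%.

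**The case against.** The restriction is openly pre-specified, and section 5 allows an efficacy analysis to depart from ITT where the SAP says so. Duration of a state is undefined for someone who never entered it, so a remitter-only duration is a legitimate description. Objective 2 uses the same words for time to first response, where never-responders have no time to average either. Counting zeros is therefore one reading of the objective, not the only one. All of this stands, and rewording the objectives is accepted below as an alternative. SAP 6.1.1 also lets the SAP override the protocol on methods. That settles precedence, but it does not make the conditional test answer the objective.

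Four stronger readings are tempting, and the documents do not support them.
- *That the plan is blind to differences in remission rate.* It is not. Week-16 and week-52 remission, maintenance from week 16 through week 52, and time to remission are all compared in ITT subjects. In the rate-difference case above, the planned time-to-remission log-rank rejects in about 60% of trials. Only the duration tables miss the difference.
- *That the tables overstate the average by 1/(proportion who remit).* That factor applies to a mean, which 6.3.3.1 does not list. Medians and quartiles do not scale in that way.
- *That the log-rank has an inflated false-positive rate.* With 20% long remissions (mean 80 weeks) against 40% short ones (mean 10 weeks), time per participant is nearly equal (6.6 and 6.3 weeks) and the test rejects in about 97% of trials. It correctly rejects its own null; the error would lie in reading the result as the stated objective.
- *That no denominators will be shown.* The table layouts are in a separate document, so this is unknown.

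Maintenance of remission does give one durability measure over all ITT subjects. But it is a yes/no outcome, requires remission at week 16 and has no counterpart for response, so it does not supply an average duration.

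**Conclusion.** The point holds in limited form. The objectives, the definitions in 2.2.3 and the ITT titles do not agree. The log-rank test of the two durations compares subsets selected by outcome, in a study whose protocol plans no formal between-group comparison. The test does not reflect differences that arise through the remission rate, and it can point towards the group with less time in remission when the other group adds shorter remissions.

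The mismatch and the test's null follow from the text alone. The size does not: the figure of about 36% in the wrong direction (8.7 against 6.2 weeks per participant), and the range of 7% to 63%, rest on assumed remission and relapse rates, an assumed equal split and no dropout. Without the pattern of more but shorter remissions, the reversal does not arise. Severity is modest: these are selected other secondary endpoints, and no decision rule depends on the p-values.

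**What to change.** 1. In SAP 6.3.3.1, delete the log-rank comparison for duration of remission and duration of response. This agrees with the protocol's statement on between-group comparisons.
2. Retitle Tables and Figures 14.2.4.2 and 14.2.4.4 as covering subjects who achieved remission, or who achieved response, show n, and keep them descriptive.
3. For objectives 1 and 3, add mean weeks in remission and in response through week 52 over all ITT subjects, with 0 for those who never reach the state. Give a 95% confidence interval overall and, descriptively, by parent group and anti-TNF use. State the rules with the definition: missed and post-dropout visits count as not in the state, consistent with 2.2 and 6.1.3; rescue use counts as failure, as in 6.1.6; how time between CDAI visits is credited; and whether later episodes count, since the present definition stops at the first loss.
4. If the sponsor wants only the conditional quantity, reword the two objectives to refer to subjects who achieve remission or response in place of item 3. Items 1 and 2 still apply.

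Cost: SAP wording, a derived variable for each state and an added row in two tables; no new data. The headline average becomes shorter because non-remitters count as 0, and two p-values are lost.
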